4.2.3 Dose modifications

Toxicity is an adverse event judged by the investigator to be possibly, probably or definitely related to study medication. All grade 1 toxicities and adverse events and tolerable unrelated grade 2 adverse events can be treated according to standard clinical practice guidelines, without dose modification.

See Table 2 for the Dose Modification Plan for patients experiencing ≥grade 2 toxicities.

Table 2. Dose Modification Plan for Treatment-Related Toxicities

NCI CTC 5.0 Criteria	Dose Modification Instructions		
Symptomatic toxicity (e.g., nausea, vomiting or diarrhea) or laboratory abnormalities (e.g, hypokalemia) ≥grade 3 which can be reduced to ≤grade 1 within 48 h with standard supportive measures	No dose modification.		
Any intolerable grade 2 toxicity	The investigator should consult the study sponsor regarding grade 2 toxicities that are considered intolerable by the patient or physician. A dose reduction may occur with prior consultation with and approval by the study sponsor.		
Any toxicity ≥grade 3 other than the	Hold study drug.		
above	Assess patient at least every 3 days.		
	If the toxicity improves to ≤ baseline within a week, restart study drug and reduce dose by one dose level (Table 3).		
	If toxicity does not improve to ≤ baseline within one week, discontinue study drug.		
	Omitted doses are not made up.		

CONFIDENTIAL: PROPRIETARY INFORMATION

Patients may undergo two step-wise dose reductions, as shown in Table 3. Only two dose reductions are allowed. If the patient still has significant toxicity, as described in Table 2, after two dose reductions, treatment is to be stopped.

Table 3. Dose Levels

Dose Level		
Starting dose	1 cap daily	2 caps qd
Reduction 1	1 cap q2 days	1 cap qd
Reduction 2	Discontinue	1 cap q2 days

In part A of the study, patients may get two bottles of capsules with the same drug (active or placebo) or one bottle of each, active and placebo. In order to dose reduce in that situation, the patient will be told to take one capsule from alternate bottles on alternate days, stopping at day 15, regardless of how many capsules are left. Generally, one capsule should remain at the end of the study, unless a capsule was accidentally damaged or lost.

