6.1 Terminology

An Adverse Event (AE) is defined as any untoward medical occurrence associated with the use of a drug in humans, whether or not considered drug related. An AE (may also be referred to as an adverse experience) can therefore be any unfavorable and unintended sign (including an abnormal laboratory finding, for example), symptom, or disease temporally associated with the use of a medicinal (investigational or marketed) product, whether or not considered related to the medicinal (investigational or marketed) product and from any route of administration, formulation, or dose, including an overdose. Worsening of baseline signs, symptoms or concomitant illnesses are also considered adverse events.

Exacerbation of COVID-19-related signs and symptoms are considered lack of efficacy, rather than adverse events. All signs and symptoms will be followed, but will be analyzed as part of the efficacy rather than safety analyses.

A Serious Adverse Event (SAE) is any untoward medical occurrence that at any dose results in any of the following outcomes:

death;

is a life-threatening adverse event (defined as an event in which the subject was at risk of death at the time of the event; it does not refer to an event that hypothetically might have caused death if it were more severe);

requires in-patient hospitalization or causes prolongation of existing hospitalization;

a persistent or significant disability/incapacity or substantial disruption of the ability to conduct normal life functions;

a congenital anomaly/birth defect;

is an important medical event. This is defined as a medical event that may not be immediately life-threatening or result in death or hospitalization but, based upon appropriate medical and scientific judgment, may jeopardize the subject and may require medical or surgical intervention to prevent one of the other serious outcomes listed in the definition above. Examples of such events include, but are not limited to, intensive treatment in an emergency room or at home for allergic bronchospasm; blood dyscrasias or convulsions that do not result in hospitalization.

If either the sponsor or investigator believes that the event is serious, the event must be considered serious and be evaluated by the Sponsor for expedited reporting.

A *suspected adverse reaction* means any adverse event for which there is a reasonable possibility that the drug caused the adverse event.

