Appendix 2. Patient diary

Patient-Reported COVID-19 Sign and Symptom Diary (PRO-COVID-19)

General information (not to be included in the actual questionnaire): Questions and response options are sorted into four separate domains based on affected system including: body/systemic, respiratory, gastrointestinal and nose/mouth/throat.

Instructions

This questionnaire asks about the impact of COVID-19 on your health. Please respond as accurately as possible.

Domain 1: Body/Systemic

	milaili i.	Doug	70ystelline	
1)	At their worst, what was the severity of your CHILLS OR SHIVERING over the last 24 hours? Chills and shivering are a feeling of coldness or shaking while not in a cold environment.			
	(\circ	None	
	(\circ	Mild	
	(\circ	Moderate	
	(C	Severe	
2)	At its wo	orst, w	hat was the severity of FEELING HOT OR FEVERISH over the last 24	
	(\circ	None	
	(\circ	Mild	
	(\circ	Moderate	
	(\bigcirc	Severe	
3)	At their worst, what was the severity of your MUSCLE OR BODY ACHES over the last 24 hours?			
	(\circ	None	
	(\bigcirc	Mild	
	(\circ	Moderate	
	(\circ	Severe	

4)	At their worst	t, what was the severity of your HEADACHES over the last 24 hours?
	\circ	None
	0	Mild
	\circ	Moderate
	0	Severe
5)		what was the severity of your TIREDNESS OR FEELING OF LOW er the last 24 hours?
	0	None
	\circ	Mild
	\circ	Moderate
	0	Severe
6)		what was the severity of your CHEST PAIN over the last 24 hours? shows the location of your chest.
	\circ	None
	\circ	Mild
	\circ	Moderate
	0	Severe
Do	main 2: Res _l	piratory
7)	At its worst, v 24 hours?	what was the severity of your DIFFICULTY BREATHING over the last
	0	None
	\circ	Mild
	\circ	Moderate
	0	Severe
8)	At its worst, v	what was the severity of your COUGH over the last 24 hours?
	0	None
	0	Mild
	0	Moderate
	\circ	Severe

Domain 3: Gastrointestinal

9)			what was the severity of your ABDOMINAL PAIN over the last 24 picture shows the location of your abdomen.
		0	None Mild
		0	Moderate Severe Abdomen
10	•		what was the severity of your NAUSEA over the last 24 hours? Nausea of needing to vomit, commonly referred to as throwing up.
		\circ	None
		\circ	Mild
		\circ	Moderate
		0	Severe
11			what was the severity of your LOSS OF APPETITE over the last 24 of appetite is not wanting to eat or drink.
		\circ	None
		\circ	Mild
		\circ	Moderate
		0	Severe
12		-	mes did you have DIARRHEA in the last 24 hours? Diarrhea is having ery and more frequent bowel movements.
		\circ	I did not have diarrhea at all
		\circ	1-2 times

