		\circ	3-4 times
		\circ	5 or more times

•	•	nes did you have VOMIT (THROW UP) in the last 24 hours? Vomiting comach contents through your mouth.
(0	I did not vomit at all
(0	1-2 times
(\circ	3-4 times
(0	5 or more times
Domain 4:	Nose	e & Throat
		what was the severity of your SORE THROAT over the last 24 hours? may be painful or feel scratchy or irritated.
(0	None
(0	Mild
(0	Moderate
(0	Severe
15)At its wo		what was the severity of your STUFFY OR RUNNY NOSE over the last
(0	None
(0	Mild
(0	Moderate
(0	Severe
16)Rate yo	ur SE	NSE OF SMELL in the last 24 hours
(0	My sense of smell is the same as usual
(0	My sense of smell is less than usual
(0	I have no sense of smell
17)Rate yo	ur SE	NSE OF TASTE in the last 24 hours
(0	My sense of taste is the same as usual
(0	My sense of taste is less than usual
(0	I have no sense of taste

GLOBAL

1)	In the past 24 hours, have you returned to your USUAL HEALTH (before your COVID-19 illness)?
	○ Yes○ No
2)	In the past 24 hours, have you returned to your USUAL ACTIVITIES (before your COVID-19 illness)?
	○ Yes○ No
3)	In the past 24 hours, what was the severity of your OVERALL COVID-19-RELATED SYMPTOMS at their worst?
	None
	O Mild
	Moderate
	O Severe
1. In the pa	Ith and Medication Assessments est 24 hours, have you experienced any other changes in health e not already been reported?
0	Yes
	No wering "Yes" will trigger a short free-text box to describe issue, and a to contact study staff if medical assistance is required immediately.
taken fo	Inter each medication (other than the study medication) you have r COVID-related symptoms today, including the amount taken over 24 hours.
OR	medication for COVID-19-related symptoms today. ne:
Dose per tablet	/capsule (of primary ingredient):
	es taken over past 24 hours (since you last filled out the questionnaire):

Upamostat for Treatment of COVID-19 Amendment 4	15 June, 2021			
Did you take any additional medications for COVID-19? Yes: \Box No: \Box				
Answering yes will trigger another set of lines to list additional medication, dosage and number of doses.				
3. What time did you take your study medication today?				
Enter time: HH:MM AM/PM				
☐Check this box if study medication was not taken				
(If time entered):				
3a. How many capsules did you take?				

CONFIDENTIAL: PROPRIETARY INFORMATION

1 capsule2 capsules

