- B. If safety is more favorable with the 200 mg daily regimen, accrual in part B will proceed with the 200 mg daily schedule.

Efficacy will be analyzed in part A but, unless there is a marked difference between the two active dose levels, will not be used to decide on dosing in part B. Similarly, pharmacodynamic parameters will be analyzed but not used to decide on dosing.

The Safety population will be used for safety analysis in this Part A DSMB analysis. Modified ITT population will be used for efficacy endpoints.

Study: RHB-107-01 Page 17 of 28

After all part A subjects complete the study, further randomization into the study will be held until the part B dose regimen is selected and the high risk or very high risk population is further defined. Analysis of part A will be reviewed by a data and safety monitoring board (DSMB). Assuming that there are no substantive negative safety signals to continuing with at least one dose level, a decision will be made regarding continuing with the current design and sample size or increasing the number of patients in part B to enable detection of a significant improvement in the incidence of hospitalization or death in the upamostat group as compared to placebo.

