## 13. Analysis of Secondary Efficacy Endpoints

Analysis population: Analysis will be performed using the mITT and PP populations.

Analysis will be performed not only of symptom resolution and occurrence of new symptoms in aggregate, but also by individual symptoms assessed by investigators as related to COVID-19. This includes both the symptoms in the questionnaire and additional, less common symptoms which are recorded on the AE reports but attributed to COVID-19.

Items 1, 2, and 4 below are first-tier secondary objectives, to be analyzed initially. Items 3, and 5 are second tier objectives, which may be reported subsequently. Comparison between active treatment and placebo of the following secondary efficacy endpoints will be performed:

- 1) Incidence of hospitalization or death: the primary assessment of this endpoint will be among patients in the high risk group. This has been defined preliminarily above. The group may be redefined and recruitment for part B restricted based on analysis at the end of part A.
  Specific COVID-19 symptoms resulting in hospitalization will be tabulated by SOC, PT and severity. Depending on the number of patients hospitalized, this may be shown either as a table or listing.
  - Specific main COVID-19 symptoms resulting in death will be listed per patient.
- 2) The proportion of patients who are PCR-negative at each time point assessed, days 8, 15, 29 and 57 from the start of treatment (landmark analysis);
- 3) Time to resolution of individual disease-related symptoms present at baseline; COVID-19 symptoms, derived from the symptom questionnaires and those events entered as related to COVID-19 on the AE tables will be summarized as well using MedDRA classification by SOC, PT and severity as new COVID-19 symptoms and those worsening on study by at least one grade
- 4) Development of new disease-related symptoms or pneumonia on study;
- 5) Changes in laboratory markers of disease severity, i.e., oxygen saturation, CRP, lymphocyte count and D-dimer levels, from baseline to time points at which these are measured on study.

The time frame for all endpoints unless otherwise stated is from Day 1 (day of first dose of study medication) through study Day 57. The time to event endpoints will be analyzed using the methods described for the primary endpoint above.

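### Part A compares tolerability between doses without any safety table of new or worsened diary symptoms, so drug effects that sites attribute to COVID-19 can drop out of the dose comparison

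*Protocol*

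**What the plan says.** **Classification.** Protocol 6.1 first gives a general rule: "Worsening of baseline signs, symptoms or concomitant illnesses are also considered adverse events". The next paragraph makes an exception: "Exacerbation of COVID-19-related signs and symptoms are considered lack of efficacy, rather than adverse events". It continues: "All signs and symptoms will be followed, but will be analyzed as part of the efficacy rather than safety analyses". Protocol 7.5 and SAP 15 repeat the exception.

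**Toxicity.** Protocol 4.2.3 defines toxicity as an adverse event that the investigator considers at least possibly related to study drug. The first row of Table 2 begins "Symptomatic toxicity (e.g., nausea, vomiting or diarrhea" and concerns grade 3 or higher events that supportive care brings down to grade 1 or less within 48 hours. It calls for no dose modification. The text above the table says the same of all grade 1 toxicities.

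**Diary.** Appendix 2 has 17 symptom items, presented to the patient as effects of COVID-19. Five are gastrointestinal: abdominal pain, nausea ("what was the severity of your NAUSEA over the last 24 hours"), appetite loss, diarrhea and vomiting. The later health-change question asks "have you experienced any other changes in health", limited to changes not yet reported.

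**Analysis.** SAP 13, an efficacy section, says: "COVID-19 symptoms, derived from the symptom questionnaires and those events entered as related to COVID-19 on the AE tables will be summarized as well". The summary covers symptoms that are new or at least one grade worse.

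**Dose decision.** Under protocol 4.8 and SAP 7, the dose choice rests on clinical judgement of the safety profiles of the two active arms. Similar safety leads by default to one named regimen. Of efficacy, SAP 7 says that it, "unless there is a marked difference between the two active dose levels, will not be used to decide on dosing in part B"; protocol 4.8 says the same.

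**The concern.** The symptoms that Table 2 uses as examples of drug toxicity are also COVID-19 diary items. Take a patient who first has diarrhea on day 4. The patient scores it in the diary and then has no further change to report at the health-change question. Whether it becomes an adverse event depends on a blinded investigator deciding that study drug is at least a possible cause, in someone with a disease that produces the same symptom. If the answer is COVID-19, the symptom is analysed as efficacy, which does not normally inform the dose.

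Part A's primary objective is at stake. If one dose causes more low-grade or quickly controlled gastrointestinal symptoms, the two doses could still look similar on the safety tables, and similarity is what triggers the default regimen.

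**Working it through.** There is no figure in the plan to reproduce. Part A's 20 patients per arm have no power basis (protocol 7.1). The check is to follow one symptom through the documents and then illustrate its size.

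**1. Following a new diary symptom that could have either cause**

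| Step | What the documents provide | Is the symptom seen as safety? |
|---|---|---|
| Diary entry | Scored under a COVID-19 item; the later prompt asks only for other changes (Appendix 2) | Not from the diary alone |
| Staff review | Adverse events are reviewed at every contact from day 3 (Table 1 and its notes) | Yes, if staff enter it as an adverse event |
| Attribution | Protocol Table 4: about equally likely is possibly related; another more likely cause is probably not related | Depends on judgement |
| Attributed to COVID-19 | Efficacy (protocol 6.1, SAP 13 and 15) | No |
| Judged at least possibly related | Adverse event and toxicity (protocol 4.2.3) | Yes |
| Leads to dose change or stop | DSMB item (a) | Yes, if recorded as an adverse event |
| Grade 1, or grade 3 or higher and controlled within 48 hours | No dose modification required (protocol 4.2.3, Table 2) | Only through attribution |

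Two points follow.

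- Protocol 1.1 says that many mild cases have only gastrointestinal symptoms, or these with mild pulmonary ones. A site applying Table 4 properly could therefore find the disease the more likely cause of a drug-caused symptom.
- DSMB item (a) is ambiguous. The related events it lists may be all related adverse events, or only those that required a dose change or stop.

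**2. What the DSMB sees of the symptoms attributed to COVID-19**

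Items (d) and (f) of its list cover disease exacerbation and efficacy. New disease-related symptoms are first tier (SAP 2.2 item 6, SAP 13 item 4), but as efficacy. The summary by system organ class, preferred term and severity is printed under SAP 13 item 3, which is second tier and may be reported later. No safety table shows diary symptoms by arm.

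**3. Illustration (all rates assumed)**

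Let d be the rate of drug-caused new diarrhea and f the share of those cases attributed to COVID-19. The expected number of patients in the adverse-event table is 20 × d × (1 − f).

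| f | 400 mg, d = 30% | 200 mg, d = 10% |
|---|---|---|
| 0 | 20 × 0.30 = 6 | 20 × 0.10 = 2 |
| 0.5 | 3 | 1 |
| 1 | 0 | 0 |

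The last row needs every case to be attributed to the disease and is an extreme.

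**4. What an attribution-free table would show**

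With a background rate b of new or worsened disease symptoms, assumed independent of drug effects, the observed rate is b + (1 − b) × d. The gap between doses is (1 − b) times the difference in d. Exact binomial results for 20 per arm:

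| Drug-caused, 200 vs 400 mg | b | Observed rates | Gap (points) | Chance of at least 5 more patients at 400 mg | Chance of Fisher p ≤ 0.05 |
|---|---|---|---|---|---|
| 5% vs 25% | 0 | 5% vs 25% | 20 | 40% | 30% |
| 5% vs 25% | 20% | 24% vs 40% | 16 | 33% | 12% |
| 5% vs 25% | 40% | 43% vs 55% | 12 | 25% | 6% |
| 10% vs 30% | 0 | 10% vs 30% | 20 | 42% | 24% |
| 10% vs 30% | 20% | 28% vs 44% | 16 | 33% | 12% |
| 10% vs 30% | 40% | 46% vs 58% | 12 | 25% | 6% |

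Background disease dilutes the signal, and the signal is weak at this size even with b = 0. Unlike the adverse-event table, however, this one does not depend on f.

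**The case against.** A reader might infer that the plan sends drug-caused symptoms to efficacy by rule, that the DSMB chooses the dose without seeing them, and that gastrointestinal upset is the drug's most likely intolerance. The documents support none of these.

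- Read in context, the 6.1 exception concerns COVID-19 symptoms. A symptom judged at least possibly drug-related stays an adverse event, and Table 4 puts an evenly balanced case on the related side.
- The diary is not the only route. Staff ask about adverse events at each contact, and nothing in the documents shows how sites usually attribute gastrointestinal complaints.
- The DSMB reviews adverse events that lead to dose change or discontinuation, serious adverse events, disease exacerbation and efficacy parameters. It is also told of each reduction or stop for toxicity as it occurs.
- Table 2 gives the three symptoms as examples only. Protocol 1.2 calls the drug very well tolerated as a single agent and in combination, and names transaminase rises and anemia, with no gastrointestinal signal. Protocol 1.3 suggests the drug may reduce gastrointestinal symptoms.
- The efficacy limit has an exception for a marked difference, and the separate DSMB charter may say more.
- Even 6 versus 2 of 20 gives a Fisher p of 0.24, and a table that mixes causes is noisier still.

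The two statements in 6.1 can also be read as a general rule with a specific exception. That is fair, but it leaves open which one governs a baseline symptom that worsens for an unclear reason.

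These points narrow the concern without closing it. Each safety route depends either on a dose change, which Table 2 often does not require, or on a causal judgement that no rule guides for symptoms with two possible causes. Lack of significance does not argue against a descriptive table, because the plan itself makes the dose choice a matter of clinical judgement.

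**Conclusion.** The point holds in a limited form. New or worsened diary symptoms that sites attribute to COVID-19 leave the safety analysis and normally do not inform the dose choice. The exposed group is symptoms that prompt no dose change, including grade 1 events and quickly controlled grade 3 or higher events. A dose-related excess among them could be missing from the comparison that is part A's primary objective.

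Its size cannot be computed from the documents, which give neither symptom rates nor attribution rates. The range from 6 versus 2 down to 0 versus 0 of 20 rests on assumed rates of 30% and 10%. The conclusion itself rests only on the text: the overlap of diary items with toxicity examples, the diary prompt, the missing attribution rule and the place of these symptoms in the analysis. The DSMB charter was not available and might already address this. The change should be made because the gap touches the primary objective and is cheap to close.

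**What to change.** 1. **Add a safety table.** In SAP 15 and in the part A DSMB list (protocol 4.8, SAP 7), add a first-tier descriptive table by arm and diary symptom. It counts patients whose symptom on days 2-15 is new, or at least one grade worse than in the baseline diary, regardless of attribution. For items scored by frequency or by level of smell or taste, state that one grade means one response category. Show adverse-event-form entries attributed to COVID-19 beside it.
2. **Give it a place.** Say that the table is part of the safety and tolerability review. Keep the existing efficacy analysis.
3. **Reconcile the text.** Bring the two statements in protocol 6.1 into line with each other and with protocol 4.2.3, protocol 4.8 and SAP 13. State how a symptom that fits both causes is to be recorded, and clarify whether DSMB item (a) covers all related events. The dose-selection rule itself stays with the sponsor and DSMB.

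**Cost.** One extra table from data already collected and a few sentences of text. The table mixes disease and drug symptoms, which dilutes any signal, and with 20 patients per arm the disease background is comparable only in expectation. It should inform clinical judgement and not be read as a formal test.

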6.2 Assessment of Causal Relationship

The following categories and definitions for assessing the causal relationship of an event to the investigational product(s) are provided as a guide for evaluating adverse events reported in this study to determine "suspected adverse reactions" that require expedited reported to regulatory agencies if they are unexpected, i.e., SUSARs, suspected unexpected serious adverse reactions. In addition to the assessment below, the aggregate number of occurrences will be considered to decide whether the event is a reportable event and requires an IND safety report.

Table 4. Relationship of Study Medication to Adverse Events

Unrelated	The study drug almost certainly (or certainly) did not cause the event. Guidelines: There is no reasonable temporal relationship of the event to the administration of drug; The pattern is inconsistent with that known for the drug; and/or There is another obvious etiology.		
Probably not	It is more likely that the event is due to another etiology than due to the study drug. Guidelines:		
related	There is no reasonable temporal relationship of the event to the administration of drug;		
	The pattern is inconsistent with that known for the drug; and/or There is another more likely etiology.		
Possibly related	It is approximately equally likely that the event is due to the study drug as it is due to another etiology. Guidelines:		
	There is a reasonable temporal relationship of the event to the study drug;		
	The drug seems as likely as other etiologies to have caused the effect		
Probably related	It is more likely that the event is due to the study drug than due to another etiology. Guidelines:		
	There is a reasonable temporal relationship of the event to the study drug;		
	The event may be consistent with a known pattern of drug (or drug class) effects;		
	The drug seems more likely than other etiologies to cause the effect;		
	The adverse event diminished upon cessation of study drug exposure or reduction in dose; and/or		
	The adverse event worsened or recurred upon unintentional re-exposure to the study drug (Intentional rechallenge for the purpose of assigning causality should not be performed.)		
Definitely	The evidence is compelling that the study drug caused the adverse event. Guidelines:		
related	There is a reasonable temporal relationship of the event to the study drug;		
	The event is consistent with a known pattern of drug (or drug class) effects;		
	The drug is far more likely than other etiologies to have caused the effect;		
	The adverse event diminished upon cessation of study drug exposure or reduction in dose;		
	The adverse event worsened or recurred upon unintentional re-exposure to the study drug (Intentional rechallenge for the purpose of assigning causality should not be performed.)		
Unknown	The data are inadequate to assign any of the above causal relationship categories to the study drug.		

